## 11.2.5 For Participants Who Consent To Another Bomedemstat Extension Study

All AEs, SAEs, and other reportable safety events must be reported by the investigator in this protocol up to the time of consenting into another bomedemstat extension trial. Laboratory values that meet criteria for reporting as AEs performed during this study will be collected in this study.

Note: Once consented to another extension study, AEs/SAEs and other reportable safety events meeting the reporting criteria of the extension study, including those considered related to study intervention, will be collected in the extension study.

## 12 ANALYSIS AND STATISTICAL CONSIDERATIONS

#### 12.1 General Considerations

Detailed methodology for summary and statistical analyses of the data collected in this trial will be documented in a Statistical Analysis Plan (SAP). This document may modify the plans outlined in the protocol; however, any major modifications of the primary endpoint definitions and/or its analysis will also be reflected in a protocol amendment. Additional statistical analyses other than those described in this section may be performed if deemed appropriate and included in the SAP.

#### 12.2 Power

There are no sample size calculations for this extension study. Sample size will be based on elective participation of patients who were enrolled into the feeder studies.

#### 12.3 Treatment Assignment and Blinding

This is an open-label study. The Investigators, other hospital personnel, patients and Sponsor will know the identity of the treatment.

Effort will be made, as appropriate, to maintain continuity of study staff who administer/evaluate various assessments at each site (i.e., physical examination, morphology/fibrosis grade review, etc.), in order to facilitate consistency of assessments within a patient.

## 12.4 Study Endpoints

## 12.4.1 Primary Endpoints

The safety and tolerability of bomedemstat will be assessed by the analysis of adverse events (AEs), as well as changes in physical examinations, vital signs and laboratory values as detailed below.

Monitoring of Adverse Events (AEs), serious adverse events (SAEs), and AEs. AEs will be
assessed from time of entry into study until EoS or ET in terms of onset, duration,
seriousness, severity and causality, using the National Cancer Institute Common
Terminology Criteria for Adverse Events (NCI CTCAE), Version 5.

- Changes in physical examinations, vital signs and laboratory values will also be assessed until EoS or ET. Information on the timing of these assessments is presented in the schedule of assessments. The following laboratory tests will be conducted:
  - o Complete blood counts (CBC) and differential
  - o Coagulation
  - o Chemistry
  - o Urinalysis

[figure not shown]
## Additionally, in **MF patients**:

• Spleen volume reduction will be assessed based on spleen volume measured by MRI (or CT where applicable) approximately every 48 weeks.

## Additionally, in **ET patients**:

• Reduction of platelet counts will be evaluated and assessed based on local laboratory measurements of platelet counts collected serially throughout the study.

## 12.4.2 Exploratory Endpoints

#### 12.5 Data Analysis

## 12.5.1 Safety and Tolerability Data Analysis

Demographics will be tabulated and summarized. Adverse events/ongoing medical event data at the time of study entry will be listed, as will Physical Examination data at time of study entry, and at subsequent visits. All characteristics at baseline such as age, weight, height and vital signs (resting heart rate, semi-supine systolic/diastolic blood pressure, respiratory rate and temperature) parameters will be tabulated and summarized.

All patients receiving at least one dose of bomedemstat will be included in the safety analysis.

Laboratory values outside the laboratory normal ranges will be summarized and assessed for change from time of study entry and Day 1 in the feeder study.

Treatment-emergent adverse events will be coded using the Medical Dictionary for Regulatory Activities (MedDRA) and summarized for the number of patients reporting the AE and the number of AEs reported. A by-patient AE data listing including (but not limited to) verbatim term, coded term, severity, and relationship to treatment will be provided.

[figure not shown]
Concomitant medications will be listed by patient and coded using the WHO drug dictionary. Medical history will be listed by patient.

Descriptive statistics (arithmetic mean, standard deviation (SD), sample size, CV (coefficient of variation), median, minimum, maximum, and number) will be calculated for quantitative safety data as well as for the differences to baseline and time of study entry, when appropriate. In addition, a shift table describing out of normal range shifts will be provided for clinical laboratory

results and physical examination results. For safety and tolerability, missing data including those not obtained because of death will be the last value carried forward.

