# **Study Conduct:**

Eligibility criteria will be assessed based on the patient's final visit in their feeder study. The first visit in the extension study is the 'Transition Visit'. Ideally, patients will commence treatment upon completion of a Treatment Period (TP) in the feeder study; however, some patients will need to transition to this extension study at differing timepoints and so the final feeder study visit and the Transition Visit will need to be linked (i.e., patients completing their feeder study at the end of a TP will enter the extension study at TP1 Day 1; patients completing their feeder study at a 'Day 85' visit will enter the extension study at TP1 Day 85) to maintain the correct visit schedule. Patients will be dosed in TPs, with each TP comprised of daily treatment with bomedemstat for 169 days. Qualifying patients may continue to receive bomedemstat for multiple TPs, each comprising an additional 169 days of treatment.

Imago BioSciences, Inc., a subsidiary of Merck & Co., Inc. Bomedemstat (IMG-7289/MK-3543)

days) post last procedure date in the feeder study.

At each Day 169 visit, a Qualification Assessment will be made to determine whether the patient is continuing to derive clinical benefit (defined as not meeting "progressive disease" criteria, as per Appendices 16.4 and 16.5 for MF and ET patients, respectively, and safely tolerating bomedemstat), thereby determining patient qualification for continued bomedemstat use *via* entry into another TP. Patients who qualify for another TP should transition without interruption in dosing. Patients who do not qualify will discontinue bomedemstat, immediately undergo an End of Treatment (EoT) visit and have the Follow-up Period End of Study (EoS) visit scheduled. If available, patients who qualify for another bomedemstat extension study can undergo an EoT visit and transition to the next extension study without the need for a Follow up Period/EoS visit.

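### Section 12.5.1 carries the last safety value forward past death with no stated stopping point, so by-visit laboratory and vital-sign summaries and fixed-timepoint shift tables can include patients who have died

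*Combined protocol and SAP*

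**What the plan says.** The missing-data rule for safety is one sentence in Section 12.5.1: "For safety and tolerability, missing data including those not obtained because of death will be the last value carried forward". It has no time limit and no exception by type of output.

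The same section defines who is analysed: "All patients receiving at least one dose of bomedemstat will be included in the safety analysis". Patients who die after their first dose therefore stay in the safety set. Three outputs are described:

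- Descriptive statistics, including sample size, for quantitative safety data, "as well as for the differences to baseline and time of study entry, when appropriate".
- Shift tables: "a shift table describing out of normal range shifts will be provided for clinical laboratory" results and for physical examination results.
- Listings of examination findings: these data will be listed, "as will Physical Examination data at time of study entry, and at subsequent visits".

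Section 12.4.1 makes these measurements part of the primary endpoint and gives an assessment window: "Changes in physical examinations, vital signs and laboratory values will also be assessed until EoS or ET".

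On duration, the Synopsis (Study Conduct) states: "Qualifying patients may continue to receive bomedemstat for multiple TPs, each comprising an additional 169 days of treatment". No maximum number of periods is given. The Synopsis also makes entry to each further Treatment Period (TP) depend on a Qualification Assessment at Day 169 of the period just completed.

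Section 12.1 leaves detailed methodology to a statistical analysis plan (SAP) that may modify the protocol. The available document contains no separate SAP text that narrows the rule.

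**The concern.** Carrying a value forward across a missed visit assumes that a value existed and was not recorded. After death no value exists. The sentence names death as a case to be filled, so this is a stated rule and not an omission that a reader has to interpret.

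In a by-visit table, the carried value adds a patient to n who was not observed and counts an old measurement again at a later date. A shift table at a fixed timepoint would likewise classify a patient who has died as normal or abnormal at that time. Long-term laboratory values and vital signs are a main product of an extension study, and they belong to its primary endpoint. Later visits are where the number actually observed matters most, and the rule can hide that number.

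**Working it through.** **Does the text stop the rule at death?** Four places bear on this.

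1. Section 12.5.1 names death as a reason for filling and sets no end.
2. The safety set in Section 12.5.1 keeps every dosed patient, so death does not remove a patient from the tables.
3. The window in Section 12.4.1, up to the End of Study (EoS) or Early Termination (ET) visit, says how long changes are assessed. It does not mention imputation. If it were read as ending the rule at death, the words about death in Section 12.5.1 would have little left to do.
4. The Qualification Assessment limits which visits ever fall due. A patient who dies in one period never qualifies for the next, so no visit in later periods was due.

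Nothing stops the carry-forward at death. However, on the plain meaning of a value not obtained because of death, the reach is at most the rest of the current period plus any closing visit.

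**Size.** The plan states no figure to reproduce. Section 12.2 has no sample-size calculation, and no death rate is given.

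Inputs:

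- N = 80 (Section 6.2, approximate).
- Period length 169 days (Synopsis).
- Annual death rate d = 2%, 5% or 10%. This is an assumption, shown as a range.

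The share of patients starting a period who die before its Day 169 is 1 − (1 − d)^t, with t = 169/365.25 = 0.463 years.

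| Assumed d | Share | Patients, if all 80 are in the period |
|---|---|---|
| 2% | 1 − 0.98^0.463 = 0.9% | 0.7 |
| 5% | 1 − 0.95^0.463 = 2.3% | 1.9 |
| 10% | 1 − 0.90^0.463 = 4.8% | 3.8 |

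These are values at Day 169; at earlier visits in the period they are smaller. They are also smaller in TP1 for patients who join part-way: "patients completing their feeder study at a 'Day 85' visit will enter the extension study at TP1 Day 85".

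**Direction.** If k of N values are carried, the tabulated mean is [(N − k) × mean of those observed + k × mean last value of those who died] / N. Take assumed platelet figures, in 10^9/L, with k = 4, N = 80 and an observed mean of 300:

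- Last value 50: (76 × 300 + 4 × 50)/80 = 287.5.
- Last value 150: (76 × 300 + 4 × 150)/80 = 292.5.
- Last value 500: (76 × 300 + 4 × 500)/80 = 310.

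The sign depends on the last values, which the documents cannot supply. In all three cases n reads 80 when 76 were observed.

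**Outputs affected.** Vital signs are affected only through the descriptive statistics, because shift tables are planned only for laboratory and examination results. A table of each patient's last observed or worst value is essentially unchanged, since carrying forward adds no new extreme. AE and SAE counts are not visit values and are not touched.

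**The case against.** The strongest reply is that the harm needs a table layout the protocol does not specify. Section 12.5.1 promises statistics when appropriate and does not say that quantitative summaries are by visit. If they show change to the last value, carrying forward simply gives the last observed value, which is acceptable. Layout and missing-data windows are normal SAP content, and Section 12.1 defers to an SAP. The study is open-label, has a single treatment and is summarised descriptively, so no test or decision is shown to turn on these tables.

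Much of this stands. It limits the consequence and the severity. It does not remove the defect, because the protocol leaves layout open but fixes the imputation rule, and that rule gives a wrong result in any by-visit table built from it.

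A reader might infer that deaths accumulate over successive periods. With all 80 patients kept from TP1 Day 1 to Day 169 of TP4 (4 × 169 = 676 days, 1.851 years), the same rates give 3.7%, 9.1% or 17.7%. The documents do not support that as the expected size. It requires tables that keep patients in periods for which they never qualified; the text does not rule this out, but it does not state it.

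A reader might also infer that the rule makes the drug look safer. No direction can be derived.

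Nor is it clear that the rule reaches patients who left through EoS or ET or moved to another extension study. Section 12.4.1 can be read as ending assessment at EoS or ET, and after transfer no further visit is due in this study.

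**Conclusion.** The concern holds as a defect in a stated rule and should be fixed. As written, Section 12.5.1 allows values after death into by-visit laboratory and vital-sign summaries and into fixed-timepoint laboratory or examination shift tables, with n above the number observed.

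On the visits that can actually fall due after a death, the affected share is about 0.9% to 4.8% of the patients in a period. That range rests on assumed death rates of 2% to 10% per year, a full 169-day period, no other exits and by-visit tables that retain patients who have died. The counts of 0.7 to 3.8 also assume that all 80 are in the period together. The share is zero if carrying forward ends at death or if tables use only last observed values.

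Confidence is high about the wording. The practical effect is conditional on table layout and on any SAP text not seen here.

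**What to change.** Replace the carry-forward sentence in Section 12.5.1, and match it in the SAP, with:

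*Laboratory, vital-sign and physical-examination data are summarised as observed, with the number of patients observed at each visit. No value is imputed after death, EoS/ET or transfer to another extension study. Deaths and discontinuations are reported separately. Any end-of-study summary uses a separately labelled last observed value per patient.*

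Base the shift tables on observed values through EoS/ET, so that results after the last dose are kept.

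This also settles the position of patients who leave or transfer. No additional data collection is needed. The cost is a smaller n at later visits. Under Section 12.1, a protocol amendment is also needed if the change counts as a major modification of the primary endpoint analysis.

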## 12.5.2 Efficacy Data Analysis

The primary efficacy objective for this study is to measure the extent and durability of bomedemstat treatment effects on the exploratory endpoints including any impact of bomedemstat on the natural history of MF and ET. The long-term effects of bomedemstat will be examined by summarizing the exploratory endpoints from feeder study baseline through the extension study.

If applicable, progression free survival (PFS), event free survival (EFS), and overall survival (OS) will be calculated using the Kaplan-Meier method.

Additionally, for **MF Patients, s**pleen volume reduction will be assessed based on spleen volume measured by MRI (or CT where applicable).

Additionally, for **ET Patients**, the below endpoints, proportions and corresponding 95% confidence intervals will be based on the Clopper-Pearson method:

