Bomedemstat Dosing: All patients will be dosed with bomedemstat daily with dose-titration contingent on the Titration Assessment performed at every TP visit. Patients receiving their first extension study dose with no interruption in dosing will have a Titration Assessment performed at the Transition Visit to determine if a titration is needed. Patients requiring an interruption in dosing will have a Titration Assessment performed at the Transition Visit to determine if they will commence at the same daily dose of bomedemstat being taken at the conclusion of their feeder study or if a down-titration or dose hold is needed (up-titrations are not permitted). Titration targets and rules, specific to the underlying MPN, are detailed in the Study Reference Manual, Pharmacy Manual, and Appendix 16.1.3 and 16.1.4. The upper limit for titration is 6 mg/kg/day.

Study Assessments: The key study assessments outlined below are also summarized in Study Assessments, Section 9, and in the Schedule of Assessments, Section 16.1.

\*Patients entering the extension study at the final visit of the feeder study will undergo the asterisked procedures in association with the feeder study; the assessments should not be duplicated. Patients entering the extension study that require interruption of dosing must undergo the asterisked procedures.

Limited Physical Examinations (LPE):

LPEs include weight, vital signs, a review of body systems to assess change from previous LPE and spleen measurement.

Bomedemstat (IMG-7289/MK-3543)

following the last assessment in the feeder study for as long as the patient continues to qualify for treatment, and at the Suspected Relapse, EoT, EoS and ET visits. Bone marrow sampling will not be repeated if performed in the prior 5 weeks.

 $^\dagger$ Aspirate sample should be optimally obtained within the first pull. Do not collect after a second pull attempt.

Local Laboratory Assessments: The following panels (Section 10.1.1 details analytes) will be performed as per below, and at the Transition Visit\*, Suspected Relapse, EoT, EoS and ET visits:

Genomic and Correlative Research Analyses: The following will be collected at the timepoints noted below, and (unless bone marrow was performed in the prior 5 weeks) at the Suspected Relapse, EoT, EoS and ET visits. Genomic mutant allele burden will be analyzed. Also, some or all of each sample may be placed in long-term storage for potential correlative research studies.

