# 4.1 Objectives

The objectives of this extension study are to:

- Continue to assess the safety, tolerability and efficacy of bomedemstat in patients who received bomedemstat in a prior study
- Measure the extent and durability of bomedemstat treatment effects on exploratory endpoints including any impact of bomedemstat on the natural history of MF and ET

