#### 9 STUDY ASSESSMENTS

This section provides comprehensive detail on the visits and assessments required and should serve as the main guidance for use during study visits. The Schedule of Assessments (Section 16.1) contains these details in tabular form and is provided for use in a supportive/reference capacity only. To maintain clarity while facilitating a modicum of brevity, the 'Terms' in Table 1 below will be utilized in this section to encompass the broader 'Protocol Meaning' as stated.

Table 1 List of Protocol Terms and Meanings

Town			
Term	Protocol Meaning		
Limited Physical Exam, including Vital Signs	• Spleen measurement. The edge of the spleen shall be determined by palpation, measured in centimeters, using a soft ruler/tape, from the costal margin to the point of greatest splenic protrusion in the midclavicular line. Measure in the same manner at all visits.		
	Weight, measured (in kg)		
	Review of body systems for changes from previous visit		
	• Vital signs, after patient has sat semi-supine for ~3 minutes, of:		
	o Heart rate		
	o Respiratory rate		
	
 
Temperature
 
		
	
 
Systolic/diastolic blood pressure
 
		
Adverse Events and Concomitant Medications Collection	Use non-directive questions (i.e., "How are you feeling") to query patient regarding AEs that may have occurred and inquire about medication changes.		
Full Local Lab Assessment	The following panels performed locally (Section 10.1.1 details analytes):		
	Hematology with automated differential		
	Biochemistry		
	Coagulation		
	Urinalysis		
	Serum pregnancy test for WOCBP		
MPN Symptom Questionnaires	IRB/EC approved questionnaires will be completed based on the version required in the applicable feeder study. For example, the MPN-SAF TSS for IMG-7289-CTP-102 and the MPN-SAF for IMG-7289-CTP-201.		
	Questionnaires will be completed weekly, ideally at the same time and day each week for consistency, through the EoS or ET Visit. The actual date of questionnaire completion, not the planned or collected date, must be documented on each questionnaire completed. On visit days, the questionnaire should be completed prior to the study visit. If the patient arrives without a completed questionnaire, the patient will complete it during the visit, and it will be collected by study staff prior to the patient departing.		

Term	Protocol Meaning	

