## **11.2** Adverse Events

The Investigator is responsible for monitoring the safety of patients who have enrolled in the study and for accurately documenting and reporting information as described in this section. Patients will be instructed to report to the Investigator any AE that they experience. Investigators will ask about the occurrence of AEs at each visit. Investigators are required to document all AEs occurring during the clinical study, commencing with the first dose of bomedemstat at the Transition Visit through to the EoS Visit (scheduled at 14 days post last bomedemstat dose). AE recording will continue for patients who discontinue study drug but remain in Follow-up Period, until their EoT and EoS Visits have been completed.

Note: Any medical event i.e., (S)AE which is ongoing from the feeder protocol study at the time of dosing with bomedemstat in this protocol must be documented in the patient's medical notes and will be recorded on the appropriate eCRF pages as AEs ongoing at the time of study entry.

New AEs will be recorded on designated eCRF pages. Each AE is to be characterised (i.e., verbatim term) and information provided regarding its seriousness, start and stop dates, intensity, outcome, and causal relationship with the study drug.

An AE is any undesirable physical, psychological or behavioral effect experienced by a patient during participation in an investigational study, in conjunction with the use of the drug or biologic, whether or not product-related. This includes any untoward signs or symptoms experienced by the patient from the time of first dose with bomedemstat under this protocol until completion of the study.

AEs may include, but are not limited to:

- Subjective or objective symptoms spontaneously offered by the patient and/or observed by the Investigator or medical staff
- Findings at physical examinations
- Laboratory abnormalities of clinical significance
- Overdose defined as any dose exceeding the prescribed dose for bomedemstat

• Potential DILI events defined as an elevated AST or ALT laboratory value that is greater than or equal to 3× the ULN and an elevated total bilirubin laboratory value that is greater than or equal to 2× the ULN and, at the same time, an alkaline phosphatase laboratory value that is less than 2× the ULN, as determined by way of protocol-specified laboratory testing or unscheduled laboratory testing.

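### By-period efficacy summaries limited to patients still on study are biased toward durability, because each Day 169 test removes patients for progression or intolerance; the size of the bias is unknown

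*Combined protocol and SAP*

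**What the plan says.** **Aim and analysis.** Section 12.5.2 gives the primary efficacy objective as to "measure the extent and durability of bomedemstat treatment effects on the exploratory endpoints"; Section 4.1 has the same aim. The method is descriptive: "The long-term effects of bomedemstat will be examined by summarizing the exploratory endpoints from feeder study baseline through the extension study". Kaplan-Meier estimates of progression-free, event-free and overall survival are planned only where applicable.

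**Who continues.** The synopsis (Section 2, Study Conduct) tests clinical benefit at every Day 169, "defined as not meeting 'progressive disease' criteria, as per Appendices 16.4 and 16.5 for MF and ET patients, respectively, and safely tolerating bomedemstat". On failure: "Patients who do not qualify will discontinue bomedemstat, immediately undergo an End of Treatment (EoT) visit". The Qualification Assessments paragraph of the synopsis words the same test as an investigator judgement of benefit against risk.

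**How long efficacy is measured.** A partly blacked-out sentence in the synopsis, evidently about marrow sampling, schedules it "following the last assessment in the feeder study for as long as the patient continues to qualify for treatment". The sentence then adds the suspected-relapse, End of Treatment (EoT), End of Study (EoS) and early-termination visits. Local laboratory panels are also due at those visits. For symptoms, Section 9 (Table 1) says: "Questionnaires will be completed weekly, ideally at the same time and day each week for consistency, through the EoS or ET Visit". Section 11.2 places EoS 14 days after the last dose. No later efficacy follow-up is visible.

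**Denominator and leavers.** Section 12.5.1 gives a safety population and carries the last value forward, for safety and tolerability only. The visible part of 12.5.2 has no efficacy analysis set and no rule for patients who have left.

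**The concern.** The exit criteria overlap with the efficacy measures. Progressive disease in MF (Appendix 16.4) is spleen growth or leukaemic transformation; in ET (Appendix 16.5) it is transformation, including to post-ET myelofibrosis. The synopsis lists disease transformation and fibrosis score as efficacy measures for all patients, and spleen volume for MF. A patient who does badly on these is removed, and beyond the exit visits contributes nothing to later periods.

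The selection repeats at every Day 169, on top of the selection at entry, which requires a completed feeder Treatment Period (TP). With about 80 patients (Section 6.2) and no control arm, the by-period summaries are likely to carry the durability claim. A mean or proportion among those still measured can hold up while the enrolled cohort worsens, so the trend partly reflects who remains.

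**Working it through.** The plan has no sample-size or power figure (Section 12.2) and no durability figure to reproduce. The structure comes from the documents; every rate below is an assumption.

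**1. Responders, exit values included.** Let *l* be the share of current responders losing response per TP and *f* the share of those who leave at that Day 169. The rest stay as non-responders and neither recover nor leave later. Everyone starts as a responder.

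- Still responding after *k* periods, of all initial responders: R(k) = (1 − l)^k.
- Non-responders still on study after three periods: S(3) = (1 − f)(1 − R(3)).
- Apparent maintenance at Day 169 of TP4, counting those who fail at that visit: R(4) / (R(3) + S(3)).

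| l | f | R(3) | S(3) | Apparent, TP4 | All initial responders, R(4) |
|---|---|---|---|---|---|
| 8% | 50% | 0.779 | 0.111 | 0.716/0.889 = 81% | 0.92^4 = 72% |
| 8% | 80% | 0.779 | 0.044 | 0.716/0.823 = 87% | 72% |
| 12% | 50% | 0.681 | 0.159 | 0.600/0.841 = 71% | 0.88^4 = 60% |
| 12% | 80% | 0.681 | 0.064 | 0.600/0.745 = 80% | 60% |

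The range is 71-87% against 60-72%. If the failing visit is left out, the apparent figure is R(4) / (R(4) + (1 − f)(1 − R(4))), which runs from 75% (l = 12%, f = 50%) to 93% (l = 8%, f = 80%).

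**2. Is a flat trend forced?** Let *a* be the chance per TP of losing response through progression (leaves) and *b* the chance of losing it without progression (stays). With r = 1 − a − b, response among all enrolled after four TPs is r^4. The observed figure at Day 169 of TP4 is r^4 / [1 − a(1 + r + r²)].

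- a = 10%, b = 0: observed 90% at every Day 169; all enrolled 0.9^4 = 66%.
- a = b = 5%: 0.656 / (1 − 0.05 × 2.71) = 0.656/0.8645 = 76%; all enrolled 66%. The observed figure starts at 90%, so the decline shows but is understated.
- a = 5%, b = 15%: 0.4096 / (1 − 0.05 × 2.44) = 0.4096/0.878 = 47%; all enrolled 41%.

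The upward bias appears in each case. A flat trend arises only when progression is the sole route of loss.

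**3. Spleen volume, as a sensitivity check.** Simulation of 400,000 patients: mean true change +3% per scan, between-patient slope SD 5-8%, measurement SD 8%, removal once the measured change from pretreatment reaches +25%, exit scan counted.

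- Starting at pretreatment volume: at the fourth scan the true mean is +12% and the measured mean +5.8% to −2.4%, a gap of about 6-14 points.
- Starting 20% below pretreatment volume: true −8%, measured about −9% to −13%, a gap of about 1-5 points. At the sixth scan the gap is about 7-19 points.

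Scans are about 48 weeks apart (Section 12.4.1): 48 × 7 = 336 days, against 2 × 169 = 338 days for two TPs. The fourth scan is thus about eight TPs in and the sixth about twelve. The model uses imaging alone, whereas Appendix 16.4 requires palpable growth with imaging as confirmation.

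**The case against.** A reader might infer that measurement stops at the failed test and that later periods must look durable. The documents do not support either reading. The failing Day 169 visit is itself measured, marrow and laboratory panels are due at EoT and EoS (marrow unless sampled in the previous five weeks), and symptom forms run to EoS. Progression is also defined narrowly. In MF, relapse is a separate category, so losing a symptom or anaemia response does not by itself fail the progression test; in ET, losing count control is not progression. Such patients can stay and pull the trend down. The benefit-risk wording of the test could widen removal, by an unknown amount.

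Progressors are not ignored either. Relapse and transformation are listed efficacy measures, and progression-free and event-free survival would count progression. But those are conditional, and they do not correct by-period summaries of spleen, fibrosis, symptoms or counts.

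Nor can it be said that the plan lacks a denominator rule. The content of Section 12.4.2 and the ET endpoint list in 12.5.2 are absent from the public text, and Section 12.1 defers detailed methods to a SAP. A rule may exist there.

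Finally, an on-treatment description is a legitimate choice for an uncontrolled extension, and counting intolerance as failure is one estimand among several. That stands. It argues for showing both summaries and labelling each.

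**Conclusion.** The concern holds in a limited form. The documents establish selection at each Day 169 on progression and tolerance, no visible efficacy follow-up beyond 14 days after the last dose, and durability judged by summarising endpoints over time. Summaries restricted to patients still on study are therefore biased toward durability.

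The direction was the same in every scenario tried; the size is illustrative. With 8-12% of responders losing response per period and 50-80% of those leaving, the overstatement after four periods is about 9 to 20 points (81% against 72% at the least, 80% against 60% at the most). It shrinks as more loss occurs without exit, and for spleen volume it depends heavily on how far below pretreatment volume patients start. None of these inputs comes from the documents. The conclusion also assumes that no denominator or exit rule sits in the unpublished text.

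**What to change.** In Section 12.5.2, unless the unpublished endpoint definitions or SAP already do so:

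1. Show every by-period summary with its n, include each leaver's EoT value as the final point, and display the same patients' earlier values grouped by last period reached.
2. Beside the on-treatment summary, report durability among all enrolled patients, or all responders, who could have reached that period. Count exits for progression or lack of benefit as not maintained. Count intolerance exits the same way in a separate, stated composite version. Censor administrative exits and transfers to another bomedemstat extension. Do this with a time-to-event estimate: dropping transferred patients from a crude denominator while keeping progressors would bias the figure downward.
3. Make progression-free survival and duration of response firm analyses with stated censoring rules.

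Item 2 needs the reason for each exit. The synopsis words the qualification test in two ways, and these passages must be reconciled so that exits can be classified consistently.

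The cost is analysis wording and a few extra tables, largely from data already scheduled for collection. Reported durability will look less favourable.
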